#### **4.4.2.7. *Numerical Rating Scale leg pain***

The Numeric Rating Scale (NRS) leg pain is a patient reported outcome and is used to measures a person's pain intensity with respect to leg pain. Subjects are to indicate on a scale from 1 to 10, the

average pain experienced in the previous week. Zero is equated to no pain and 10 equates to worst pain possible. The NRS leg pain will be collected on paper after which it will be entered into the eCRF.

#### **4.4.2.8. *Analgesic Use***

Current analgesic use will be recorded at screening, 12 months and 24 months. The analgesic use questions as described by Clement *et.al.*[44]will be used to collect this information. Subjects will be asked if they use narcotic or non-narcotic pain relieving medication for their back problems, “yes regularly”, “yes sometimes”, or “no”.

#### **4.4.3. Pre-surgery phase**

##### **4.4.3.1. *Pre-SPSI™ Surgical Plan***

After the screening visit, the investigator will complete an pre- SPSI™ surgical plan. This pre- SPSI™ surgical plan will document the type of operation (decompression or decompression plus fusion) that would be performed at the operative level based on the investigator’s standard of care decision making. This pre- SPSI™ surgical plan will be entered by the investigator into the eCRF and collected by the CRO managing the study. This surgical plan must be provided to the CRO before the SPSI™ report is provided to the investigator.

##### **4.4.3.2. *SPSI™ Report***

The preoperative flexion-extension radiographs will be sent to MMI and the intervertebral motion will be analyzed using QMA®. To avoid any possibility of bias, MMI will not be informed what level the investigator intends to treat. Every level in the lumbar spine, from L1-L2 to L5-S1 will be analyzed. If there is insufficient intervertebral motion to reliably calculate SPSI™(< 5 degrees), or if there is excessive out-of-plane, or if not the entire spine was captured in either the flexion or extension radiograph, or if there was any other image quality problem that prevents a reliable calculation of SPSI™, then the SPSI™ for that level will be recorded as “NA” (not analyzable). When the site receives the SPSI™ report, the investigator will determine whether SPSI™ is reported at NA at the level the investigator had intended to treat. These subjects will be withdrawn from the clinical investigation and the end of the pre-surgery phase and will not receive any follow-up. In the event of subject being withdrawn from the study as a result of SPSI™ being reported as NA, the flexion/extension protocol will be re-reviewed with the site to determine if interventions can be implemented at the site to avoid further situations where SPSI™ cannot be reliably calculated.

A SPSI™ report that provides SPSI™ will be completed and returned to the investigator after 24h, but within 3 business days of receipt of the flexion-extension radiographs at MMI and recording of the initial pre-SPSI™ surgical plan at the CRO.

##### **4.4.3.3. *Post- SPSI™ Surgical Plan***

Based on review of the SPSI™ report, the investigator will determine if the pre-SPSI™ surgical plan needs to be modified as described in Table 1 of this clinical investigation plan. The investigator will review any modifications to the pre-SPSI™ surgical plan and integrate the information in the SPSI™ report along with their knowledge of the spine motion metrics and all other information that they obtain from the available imaging (MRI, CT, radiographs as per their standard clinical practice) to make a decision about

which levels to treat and what operation to perform at the stenotic level. The investigator will then complete a post-SPSI™ surgical plan. By comparing the post-SPSI™ surgical plan with the pre-SPSI™ surgical plan, a determination will be made, per Table 1, whether the SPSI™ report resulted in a change in the surgical plan. Those data will be used to address the primary endpoint: What proportion of surgical treatment plans were changed after integrating SPSI™ metrics into the planning process.

In addition, if the post-SPSI™ surgical plan is inconsistent with the SPSI™ report (e.g. SPSI™ report indicates instability but the investigator plans to decompress only, or SPSI™ report indicates stability but the investigator plans to decompress and fuse), the investigator will be asked to record the reason (e.g. SPSI™ report indicates instability but there is a contraindication to fusion; or SPSI™ report indicates stability but there is excessive fluid in the facet joint, suggesting instability, so level will be fused). If the post-SPSI™ surgical plan is inconsistent with the SPSI™ report, the subject will exit the study after the surgery has been performed

#### **4.4.4. Visit 2 - Surgery**

Surgery will be performed according to the post-SPSI™ surgical plan . Decompression and fusion surgery will be conducted according to standard hospital procedures. After the surgery is complete, the investigator records any deviations and reason for deviations from the post-SPSI™ surgical plan. For example, whereas the investigator may have planned to only decompress a level, they may find during surgery that a more extensive decompression was required than originally anticipated, and that requires fusion to avoid iatrogenic instability. Deviations from the post-SPSI™ surgical plan are not considered protocol deviations. Additionally, details of the surgical procedures are collected.

#### **4.4.5. Visit 3 – 6 months ( $\pm 30$ d) follow-up**

At 6 months ( $\pm 30$ d) after surgery the subjects will undergo the following assessments:

- **Oswestry Disability Index**
  - ODI will be collected as described in section 5.4.2.6.
- **Numeric Rating Scale Leg pain**
  - NRS leg pain will be collected as described in section 5.4.2.7.
- **Patient satisfaction**
  - Subjects will be asked if they are “satisfied”, “uncertain”, or “dissatisfied” with surgery outcome.

This visit can be performed over the phone.

#### **4.4.6. Visit 4 – 12 months ( $\pm 30$ d) follow-up.**

At 12 months ( $\pm 30$ d) after surgery the subjects will undergo the following assessments:

- **Flexion/extension X-rays**
  - Flexion/extension X-rays will be collected at the 12 month follow-up visit for all patients as described in section 5.4.2.5.
- **SPSI™ metric**

- The 12 month flexion-extension radiographs will be sent to MMI and the intervertebral motion will be analyzed using QMA® and the SPSI™ metric will be calculated. The 12 month SPSI™ metric will be used to document whether the decompression procedure changed the stability of the treated level in subjects who underwent decompression surgery only. Additionally, in subjects who underwent decompression and fusion surgery, the intervertebral rotation will be used to determine whether the fusion was successful at stopping motion between vertebrae. A level will be classified as fused if intervertebral rotation is < 2 degrees at the operated level and > 5 degrees at an adjacent level, and will be classified as not fused if rotation is ≥2 degrees[45]. It is expected that a proportion of patients will be considered indeterminate due to insufficient patient effort and those will not be included in the data analysis.
- **Oswestry Disability Index**
  - ODI will be collected as described in section 5.4.2.6.
- **Numeric Rating Scale Leg pain**
  - NRS leg pain will be collected as described in section 5.4.2.7.
- **Patient satisfaction**
  - Subjects will be asked if they are “satisfied”, “uncertain”, or “dissatisfied” with surgery outcome.
- **Assessment of any reoperations.**
  - The occurrence of any reoperations will be recorded along with the general type of reoperation (surgery at the originally treated levels or at the adjacent levels).
- **Analgesic use**
  - Current analgesic use of pain medication will be recorded at screening, 12 months and 24 months of the clinical investigation. Subjects will be asked if they use narcotic or non-narcotic pain relieving medication for their back problems, “yes regularly”, “yes sometimes”, or “no”.
- **Assessment of adverse events**
  - Occurrence and assessment of all AEs will be recorded.

#### **4.4.7. Visit 5 – 24 months (±30d) follow-up**

At 24 months (±30d) after surgery the subjects undergo the following assessments:

- **Oswestry Disability Index**
  - ODI will be collected as described in section 5.4.2.6.
- **Numeric Rating Scale Leg pain**
  - NRS leg pain will be collected as described in section 5.4.2.7.
- **Patient satisfaction**
  - Subjects will be asked if they are “satisfied”, “uncertain”, or “dissatisfied” with surgery outcome.
- **Assessment of any reoperations.**
  - The occurrence of any reoperations will be recorded along with the general type of reoperation (surgery at the originally treated levels or at the adjacent levels).
- **Analgesic Use**

- Current analgesic use of pain medication will be recorded at screening, 12 months and 24 months of the clinical investigation. Subjects will be asked if they use narcotic or non-narcotic pain relieving medication for their back problems, "yes regularly", "yes sometimes", or "no".
- **Assessment of adverse events**
  - Occurrence and assessment of all AEs will be recorded.

#### **4.4.8. Activities Performed by Sponsor Representatives**

The sponsor of the clinical investigation (Medical Metrics Diagnostics, Inc) will work with MMI to provide investigators, X-ray technicians, and subjects with training materials. MMI will also be responsible for managing transfer of flexion-extension radiographs from the clinical sites to MMI where the QMA and calculation of SPSI™ will be performed using previously validated methods. MMI will be responsible for getting the SPSI™ report to the clinical site and for addressing any difficulties that the investigators encounter with the SPSI™ reports.

### **5. STATISTICAL CONSIDERATIONS**

Data analysis will be independently performed at MMDx and by a statistician independent of MMI. Discrepancies will be reviewed and resolved by the independent statistician. This will be done to reduce any potential errors.

#### **5.1. Primary Endpoint**

##### **Proportion of surgical treatment plans changed after including SPSI™ metrics**

The primary endpoint is the proportion of lumbar spinal stenosis treatment plans that change when SPSI™ results are used in establishing the surgical plan. The proportions will be analyzed using a statistical test for proportions. The hypothesis to be tested is that SPSI™ will result in a change in surgical plan for at least 15% of subjects.

Three lumbar spinal stenosis treatment plans (surgical plans) will be identified per the following table:

TABLE 3. DESCRIPTION OF SURGICAL PLANS

Surgical Plan	Description
P1	Pre-SPSI™ surgical plan
P2	Post-SPSI™ surgical pl
P3	Actual surgery performed

The primary endpoint will be investigated using the proportion of P2 surgical plans that changed relative to the P1 plan. This describes the proportion of surgical treatment plans that appeared to change by inclusion of the SPSI™ metric. The primary endpoint analyses will be done using the Per-algorithm Population, defined as enrolled subjects who received surgery, where the post- SPSI™ surgical plan is in accordance with the SPSI™ metric and who do not have any major protocol deviations.

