## 3. OBJECTIVE AND HYPOTHESIS

The primary objective of this clinical investigation is to determine if the SPSI™ metric calculated from preoperative flexion-extension radiographs will change the surgical treatment plan that was initially recorded before accessing the SPSI™ data.

The associated hypothesis is that use of SPSI™ will provide an objective stability metric that will change the surgical plan in a significant proportion of subjects. These changes can include the decision to fuse a level that was previously planned to only be decompressed, or to decompress a level that was previously planned to be decompressed and fused.

As a secondary objective of the current clinical investigation, clinical outcome data will be collected to test the hypothesis that the use of the preoperative SPSI™ at the treatment level will result in improved clinical outcomes. The sample size for the current study is unlikely to be sufficient to test this hypothesis with a high level of statistical power, yet the data will help with design of subsequent research.

The outcomes from this clinical investigation will serve as input for a subsequent clinical investigation to investigate the hypothesis that planning surgical treatment using the preoperative SPSI™ at the treatment level(s) will result in improved clinical outcomes and a reduction in healthcare costs.

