#### **4.3.8. Number of Subjects**

A total of 65 "treated per algorithm subjects" will be included. A subject is considered "treated per algorithm" if the post- SPSI™ surgical plan is in accordance with the SPSI™ report and if the subject has received surgery. Each clinical site contributing to the clinical investigation is expected to enroll at least 20 subjects.

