#### **5.5. Sample Size**

The primary endpoint will be investigated using the proportion of surgical plans recorded after integrating SPSI™ metrics that changed relative to the surgical plan recorded prior to accessing the SPSI™ metrics. Since all of the investigators will have extensive experience with the surgical treatment of lumbar spinal stenosis patients, it is reasonable to assume that each individual surgeon would consistently generate the same treatment plan if they managed the same patient at multiple visits. published data was found documenting this assumption, but the clinicians tend to agree with that assumption.

Nevertheless, we will allow for the possibility that 10% of treatment plans could differ if surgeons were to generate treatment plans at multiple visits. Further, we will assume that for the SPSI™ metrics to be accepted as clinically effective, then at least 15% of treatment plans would need to be changed by inclusion of SPSI™ metrics. With alpha = 5% and power = 90%, a simple test of proportions indicates that a sample size of 59 patients would be required to determine if the proportion of treatment plans changed after including SPSI™ metrics was at least 25% assuming that 10% of treatment plans could change due to variability in how surgeons establish treatment plans (Stata/IC ver 15, StatCorp, College Station, TX).

To allow for up to 7 patients that need to be dropped from the analysis for various reasons, up to 65 patients that meet all inclusion and exclusion criteria will be entered into the study to assure at least 59 patients in the final data analysis. Each clinical site contributing to the study must aim to enroll at least 20 patients.

Note that this sample size requirement assumes that the investigators will follow any changes in surgical plan that the SPSI™ metrics would support. Since investigators can choose to reject the changes supported by the SPSI™ metrics, additional subjects will be enrolled to replace those where the investigator chose to reject any SPSI™ -based changes.

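### The primary hypothesis in section 5.1 (at least 15% of plans changed) is not the test that section 5.5 sizes (10% against a true 25%), and no null, test or success rule is stated

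*Combined protocol and SAP*

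**What the plan says.** Section 5.1 defines the primary endpoint as the proportion of P2 (post-SPSI) plans that differ from P1 (pre-SPSI) plans. On the analysis it says "The proportions will be analyzed using a statistical test for proportions", and on the hypothesis, "The hypothesis to be tested is that SPSI™ will result in a change in surgical plan for at least 15% of subjects". It describes the measured quantity with some caution: "This describes the proportion of surgical treatment plans that appeared to change by inclusion of the SPSI™ metric". No background is subtracted, and no null, alpha, sidedness or decision rule appears there. Section 3 gives no number, only a metric "that will change the surgical plan in a significant proportion of subjects".

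Section 5.5 allows that 10% of plans might differ if surgeons simply planned again. It then says that "for the SPSI™ metrics to be accepted as clinically effective, then at least 15% of treatment plans would need to be changed". With alpha 5% and power 90%, it needs 59 patients to determine whether the proportion changed "was at least 25% assuming that 10% of treatment plans could change due to variability in how surgeons establish treatment plans".

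On numbers entered, 5.5 says: "To allow for up to 7 patients that need to be dropped from the analysis for various reasons, up to 65 patients", so as to leave at least 59 for analysis. There the 65 are patients who meet the eligibility criteria. In section 4.3.8 the 65 are subjects treated per algorithm.

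**The concern.** Three percentages (10, 15 and 25) are attached to one endpoint, and the plan never says which one the final analysis must exclude. An analyst who takes 5.1 at its word would test the raw proportion against 15%, a test that was never sized. An analyst who follows 5.5 would test it against 10%, and the wording there invites the conclusion that 25%, or the 15% effectiveness threshold, had been shown.

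The choice can reverse the verdict on the same count. Section 5 has the data analysed separately at the sponsor and by an independent statistician. Section 5.8 has the plan-change proportion monitored throughout. The null should therefore be fixed before the counts are known. Section 4.1.2 also uses this endpoint to judge whether SPSI is worth pursuing.

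**Working it through.** **Inputs.** From 5.5: alpha 5%, power 90%, background 10%, target 25%, n = 59, up to 65 entered, up to 7 lost. From 5.1: 15%, on the raw P2-versus-P1 proportion. Sidedness and the type of test are not stated.

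**1. Reproducing n = 59.** One-sample normal-approximation (score) formula:

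n = [(z_α·√(p0(1−p0)) + z_β·√(pA(1−pA))) / (pA−p0)]²

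- p0 = 0.10, pA = 0.25, two-sided 5%: [(1.960×0.3000 + 1.2816×0.4330)/0.15]² = 58.06, rounded up to **59**.
- The same, one-sided: [(1.645×0.3000 + 1.2816×0.4330)/0.15]² = 48.85, rounded up to 49.

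So 59 is right for 10% against 25%, and it implies a two-sided test. Formula power at 59 is 90.4%.

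**2. Power if 15% is the null for the raw proportion (true 25%, two-sided 5%).**

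- Formula at n = 59: Φ[(0.10×√59 − 1.960×√(0.15×0.85))/√(0.25×0.75)] = Φ(0.158) = 56%.
- Binomial, score cut-off 15/59: P(X≥15 | 0.25) = 52%. The upper tail at 15% is 0.0252.
- Binomial, exact 2.5% tail, cut-off 16/59: power 40%. The upper tail at 15% is 0.0115.
- Formula n for 90% power: [(1.960×0.3571 + 1.2816×0.4330)/0.10]² = 157.4, rounded up to 158.

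**3. What rejecting 10% shows at n = 59.** The cut-off depends on the test, which the plan does not name.

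| Test of 10%, two-sided 5% | Cut-off | Upper-tail error | Power at 25% |
|---|---|---|---|
| Score | 11/59 (18.6%) | 3.1% | 90.3% |
| Exact, 2.5% per tail | 12/59 (20.3%) | 1.3% | 83.6% |

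At 11/59 the Wilson 95% interval is 10.7% to 30.4%, which excludes neither 15% nor 25%. The result is 18.6 − 10 = 8.6 points above the assumed background. The Wilson lower limit is 14.7% at 14/59 and 16.1% at 15/59, so 15/59 is the first count whose interval excludes 15%. Excluding 25% takes 22/59 (lower limit 26.1%).

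With the score test, 11 to 14 changed plans out of 59 therefore reject 10% while 15% stays inside the interval. The probability of such a result is 38.3% at a true 25%.

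**4. Number analysed between 59 and 65.** The score cut-off for 10% is 11 for n = 59 to 63, and 12 at 64 and 65. The upper-tail error at 10% rises from 3.1% (n = 59) to 4.7% (n = 63) and is 2.6% at n = 65. Adding the lower tail (rejection at 0 or 1 changed plans), the total error is 5.1%, 5.4% and 5.7% at n = 61, 62 and 63.

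**5. Drop-out allowance.** 65 − 7 = 58, one short of 59. Formula power at 58 is 89.98%.

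**The case against.** The strongest reply is that the figures do reconcile. Section 5.5 speaks of 15% of plans changed by including SPSI, and 5.1 of a change that SPSI will result in. The caution in 5.1 that plans only appeared to change suggests that the raw proportion is known to contain background. On that view 10% + 15 points = 25% raw, and 5.5 supplies the alpha, power and reference rate needed to recover the test. This reading is plausible, and it stands as an explanation of where 25% comes from. It does not supply a decision rule, because 5.1 neither subtracts a background nor says that its 15% is net. On the same reading, rejecting 10% still shows only a raw rate above 10%.

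It is also fair that rejecting a null never proves the alternative used for power, in any trial. The gap in step 3 is partly that general fact. It matters here because 5.5 words the 25% as something the test would determine, and makes 15% a condition for clinical effectiveness.

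A reader might infer more than the documents support:

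- **That 59 is miscalculated.** It is not; it is correct for 10% against 25%.
- **That the trial is underpowered and needs 158 patients.** That follows only if 15% is the null for the raw proportion, which 5.1 suggests but does not state.
- **That 11/59 would necessarily count as success.** No test is named, and a two-sided exact test needs 12/59.
- **That a claim of 15% or 25% will be made.** The wording permits it but does not commit anyone to it.

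Finally, the plan calls this a pilot meant to inform later research, and sections 4.1.7 and 5.5 replace several kinds of lost subject. That makes the 65-minus-7 point one of wording only.

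**Conclusion.** Wrong as written. This is an inconsistency between the stated hypothesis and the sample-size basis, not an arithmetic error. The 90% power belongs to a test of 10% that 5.1 does not state. The hypothesis that 5.1 does state, if 15% is taken as a null on the raw proportion, has about 56% power by formula at 59 patients and a true 25% (52% binomial with the score cut-off, 40% exact). If the sized test is the one used, a positive result supports only that the raw rate exceeds 10%. With the score test, 38% of trials at the planning rate of 25% would reject 10% without excluding 15%.

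These figures assume a two-sided 5% level (inferred from n = 59), 59 subjects analysed unless another n is given, and independent plans with a common change rate. They say nothing about how selection into the Per-algorithm Population affects that rate.

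**What to change.** State one null, sidedness, named test and success rule in 5.1, and align 5.5 with it. The sponsor should choose between two options.

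**Option A, which matches the sizing.** H0: p = 10% for the raw P2-versus-P1 proportion, two-sided 5%, with the test named.

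- Score test: cut-off 11/59, upper-tail error 3.1%, power 90%. Give the cut-off and actual error for the number finally analysed, since the upper-tail error reaches 4.7% at n = 63 and the total exceeds 5% at n = 61 to 63.
- Exact test: cut-off 12/59, power about 84%.
- Either way, limit the claim to a rate above the assumed 10% plan variability, report the 95% interval, and say separately whether its lower limit exceeds 15%.

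**Option B.** Keep 15% as the null for the raw proportion and restate power at n = 59 and a true 25% as about 52% to 56% with the score test (40% exact). Restoring 90% would take 158 patients by the formula.

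**Under either option:** reword 5.5 so that 25% is the planning alternative and not something the test determines. Say whether the 15% effectiveness threshold is raw or net of the 10% background.

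**Minor:** change the allowance from 7 to 6, and define the 65 the same way in 5.5 and 4.3.8.

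**Cost.** Option A with the score test needs only rewording and no extra patients, but supports a narrower claim; the exact test also lowers the stated power to about 84%. Option B keeps the 15% bar, at the price of declaring low power or enlarging the trial.

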#### **4.1.7. Subject Replacement**

Subjects that are enrolled but who fail screening, or where the post-SPSI™ surgical plan is not in accordance with the SPSI™ metric (either because the investigator chooses not to follow the SPSI™ metric, or the SPSI™ for applicable level will be recorded as “NA”), or do not receive surgery, will be replaced.

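### The primary analysis keeps only subjects whose post-SPSI plan agrees with SPSI, so once changes are rejected it generally estimates neither the actual nor the algorithm-applied plan-change rate

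*Combined protocol and SAP*

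**What the plan says.** Section 5.1 defines the measure: "The primary endpoint will be investigated using the proportion of P2 surgical plans that changed relative to the P1 plan". It then fixes the analysis set: "The primary endpoint analyses will be done using the Per-algorithm Population, defined as enrolled subjects who received surgery", with two further conditions: P2 must agree with SPSI, and there must be no major protocol deviation.

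Other sections build the sample around that set:

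- Section 4.1.7 lists who is replaced: "Subjects that are enrolled but who fail screening, or where the post-SPSI™ surgical plan is not in accordance with the SPSI™ metric", among others.
- Section 4.3.8 counts a subject toward the 65 only if the post-SPSI "surgical plan is in accordance with the SPSI™ report and if the subject has received surgery".
- Section 4.4.3.3 says: "If the post-SPSI™ surgical plan is inconsistent with the SPSI™ report, the subject will exit the study after the surgery has been performed". It expects this to happen, because "the investigator will be asked to record the reason (e.g. SPSI™ report indicates instability but there is a contraindication to fusion", with a second example given.
- Section 5.5 states: "Note that this sample size requirement assumes that the investigators will follow any changes in surgical plan that the SPSI™ metrics would support", and adds that "additional subjects will be enrolled to replace those where the investigator chose to reject any SPSI™ -based changes".

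Section 5.6 lists two populations for the primary and secondary endpoints. One is a Safety Population that keeps every operated subject, whether or not SPSI was followed. It does not say which result decides the hypothesis.

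**The concern.** Under Table 1, a subject whose P1 disagrees with SPSI should change. If the surgeon declines and keeps P1, the primary outcome is no change, and that same fact removes the subject from the primary set. A subject whose P1 already agreed with SPSI stays in unless the plan moves away from SPSI. Inside the set, changed therefore means only that P1 disagreed with SPSI, and the two kinds of subject enter under different conditions.

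The documents give the proportion two purposes. Sections 4.1.2 and 4.1.3 use it to judge whether SPSI is worth pursuing and whether investigators will act on it, which calls for the actual change rate. The synopsis and section 4.1 speak of change when the algorithm is applied, which calls for the algorithm-applied rate. A figure that omits the plans where surgeons declined does not show the first directly, and it does not recover the second either.

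**Working it through.** **Plan's own figure.** Section 5.5 uses 10% against 25%, alpha 5%, power 90%. The two-sided one-sample normal formula gives n = [(1.960·√(0.10·0.90) + 1.282·√(0.25·0.75)) / 0.15]² = 58.06, rounded up to 59, as stated. At n = 59 the smallest count significant against 10% in a two-sided 5% score test is 11. Exact power at 25% is P(X ≥ 11) = 90.3%; the exact upper-tail probability at 10% is 3.1%.

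**Notation.** d = share of P1 plans that disagree with SPSI; q = share of those supported changes that are rejected with P1 kept; C = share of all subjects whose plan is changed away from SPSI. Let A = d(1−q) and R = dq. Then:

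- actual rate = A + C
- algorithm-applied rate = d
- section 5.1 result = A / (1 − R − C)

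The documents give no value for q or C, so the values below are assumptions. d = 25% is the design alternative in section 5.5.

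**C = 0, d = 25%**

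| q | R | Actual | Section 5.1 result | Algorithm-applied |
|---|---|---|---|---|
| 0 | 0 | 25.0% | 25.0% | 25% |
| 10% | 0.025 | 22.5% | 0.225/0.975 = 23.1% | 25% |
| 20% | 0.050 | 20.0% | 0.20/0.95 = 21.1% | 25% |
| 40% | 0.100 | 15.0% | 0.15/0.90 = 16.7% | 25% |

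For q of 10% to 40%, the result exceeds the actual rate by 0.6 to 1.7 points and falls short of the algorithm-applied rate by 1.9 to 8.3 points. With C = 0 and q strictly between 0 and 1, it always lies between the two. The gap widens with d: at d = 50% and q = 40% the three rates are 30.0%, 0.30/0.80 = 37.5% and 50%.

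**Sign reversal.** Take A = 0.20 and R = 0.10 (q = 0.10/0.30 = 33%). At C = 0.03 the actual rate is 23.0% and the section 5.1 result 0.20/0.87 = 23.0%, so the excess is gone. At C = 0.05 the actual rate is 25.0% and the result 0.20/0.85 = 23.5%.

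**Effect on the test, C = 0.**

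- Actual rate 10%: q = 20%, 50%, 67% means d = 12.5%, 20%, 30%. The section 5.1 result becomes 10.3%, 11.1%, 12.5%, and P(X ≥ 11 of 59) goes from 3.1% to 3.6%, 5.8%, 11.3%.
- Actual rate 15%, the threshold in the section 5.1 hypothesis: the critical count is 15. For q = 20%, 40% the result is 15.6%, 16.7%, and P(X ≥ 15 of 59) goes from 2.5% to 3.4%, 5.7%.

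**The 10% null as plan variability.** Section 5.5 justifies 10% as surgeons' inconsistency between visits, which can go either way. If each plan switches at random with probability 0.1, the section 5.1 result is 0.1d / [0.1d + 0.9(1−d)].

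| d | Section 5.1 result | P(X ≥ 11 of 59) |
|---|---|---|
| 25% | 3.6% | <0.01% |
| 40% | 6.9% | 0.2% |
| 50% | 10.0% | 3.1% |
| 60% | 14.3% | 21.5% |

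Under that null the test is conservative unless more than half of P1 plans disagree with SPSI. A raised false-positive rate is therefore not established in general.

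**The case against.** The strongest reply is that the plan already produces the missing figure. Section 5.6 names the Safety Population for the primary endpoint, and sections 4.1.1 and 4.4.3.3 require a reason for every rejection. The actual rate among operated subjects can be computed from planned data. This stands, and it limits the damage. It does not settle the matter, because section 5.1 assigns the primary analysis to the Per-algorithm Population alone and section 5.6 does not say which result decides.

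A second reply is that the restriction is deliberate and disclosed, since the objective is change when the algorithm is applied. But dropping rejections does not give that rate either: at d = 25% and q = 20% it gives 21.1%, not 25%. The two agree only in special cases, such as no rejections and no moves away, or moves away from SPSI among agreeing plans at the same rate as rejections among disagreeing ones.

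A third reply is that the excess over the actual rate is small. That is true at low rejection: 0.6 to 1.7 points, against a standard error of about 5 points at n = 59 and a rate of 20% (√(0.20·0.80/59) = 0.052). The eligibility criteria and investigator training may also keep rejections few. Nothing in the documents bounds the rejection rate, however, so a small bias cannot be assumed.

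Finally, counting rejections as unchanged serves the actual rate and moves further from the algorithm-applied rate. This is fair, and it is why the target has to be stated.

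**Conclusion.** The concern holds. The primary set is defined by a condition tied to the outcome, and replacement fills the sample with subjects who meet it. With rejections, the reported proportion generally equals neither rate that the documents describe. Against the algorithm-applied rate it is too low when no plan moves away from SPSI. Against the actual rate it is too high when rejections keep P1 and few plans move away, and the sign can reverse. With no rejections and no moves away there is no error.

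The size depends on assumed rejection rates. The study is described as a pilot in section 5.2, the reasons for rejection are recorded, and a Safety Population analysis is planned. The flaw is therefore recoverable and should be corrected before the analysis.

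**What to change.** - In section 5.1, define the primary set as all eligible subjects with a recorded P1, an analyzable SPSI at the treated level and a recorded P2, whether or not P2 follows SPSI. At minimum, use Safety Population subjects with an analyzable SPSI.
- Count any P2 that differs from P1 as changed, and a rejection that keeps P1 as unchanged. Report the numbers of rejections and of moves away from SPSI.
- Keep the per-algorithm result as supportive. Replacement may continue for the clinical outcome endpoints, with replaced subjects staying in the primary denominator.
- State in sections 5.1 and 5.6 which analysis decides, and whether the target is the actual or the algorithm-applied rate. Reporting Table 1 against P1 in the same set would give the latter directly.

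**Cost.** No new data: P1 and P2 are recorded before surgery. The proportion will probably be lower if rejections keep P1, and power must be restated because section 5.5 assumes full adherence. Taking 25% as the full-adherence rate, C = 0, a test against 10%, and total n = 59/(1−R) or 65/(1−R) rounded up and treated as fixed:

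| q | Actual | Proposed set, 59 per-algorithm reached | Proposed set, 65 reached | Current analysis, n = 59 |
|---|---|---|---|---|
| 10% | 22.5% | n = 61, 84% | n = 67, 85% | 83% |
| 20% | 20.0% | n = 63, 74% | n = 69, 75% | 72% |
| 40% | 15.0% | n = 66, 28% | n = 73, 30% | 39% |

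The critical counts are 11, 11, 12 for n = 61, 63, 66 and 12, 12, 13 for n = 67, 69, 73. At 10% to 20% rejection the loss from 90% comes from the rejections, not from this change. At 40% the proposed set has less power, because the per-algorithm rate exceeds the actual one.
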